ENDPOINT 1: The primary objective is to determine the feasibility and acceptability of the STAMP+CBT app. Specifically, we will evaluate patients' adherence to daily and weekly comprehensive symptom self-assessments within the STAMP+CBT app. We will calculate patients' overall adherence rate and 95% confidence interval. Defined using precision analysis, we will consider the intervention to be **feasible** if $\geq 70\%$ of subjects complete any activity on the app at least 50% of days on study. The intervention will be considered **acceptable** if $>80\%$ of the sample rate the app as satisfactory and useful (4 or higher/5); lower ratings will lead to app and content refinements. Other feasibility measures will assess time to accrual participation rates, and study retention and completion rates. Other acceptability outcomes will be assessed through qualitative debriefing interviews with patients evaluating the perceived benefits, usefulness, and satisfaction of the app, and quantitative acceptability ratings of the app's functionality, perceived utility, ease of use, and content relevance. Power calculation: with 35 evaluable patients, we will be able to estimate these proportions with margins of error (half of a 95% confidence interval) of approximately 18% or less assuming that the feasibility threshold of 70% is reached. This margin of error is small enough so that proportion estimates relevant to study feasibility will be accurate and provide informative guidance for future, larger studies. Using qualitative framework analysis methods, we will explore barriers/facilitators, suggested changes to content, acceptability of intervention engagement, and whether app use continues after completion. Although power is not sufficient in this pilot, we will explore associations between levels of engagement and changes in pain severity/interference, opioid use, catastrophizing, sleep, mood, and pain self-efficacy.

The study team will use qualitative and quantitative results to determine the comprehensive feasibility and acceptability of the pain CBT mobile health app for patients with cancer. This feasibility study will inform final modification to the application and study procedures in preparation for a future efficacy study of the STAMP+CBT mobile health app.

B. Background and Significance

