We have completed initial user acceptability testing of the app with patients from our target population (n=6) at the SCC (OUHSC IRB # 13-725) testing the app at home for 2-4 weeks. We are also currently completing pilot testing of the app with patients with advanced cancer at the DFCI in Boston, MA (DFCI IRB #21-719). Study procedures outlined in this protocol parallel those approved in DFCI IRB #21-719 protocol (currently enrolling). At this time, 5 patients have been enrolled in the study, we are recruiting 10 more patients to complete testing of the app at home for 4 weeks, in addition to completing survey assessments – similar to those outlined in this protocol. Patients who have tested the app to date (DFCI pilot, n=3; SCC pre-pilot, n=5) have reported finding the app easy to use (5-Point Likert scale for all items: DFCI=4.33; SCC=4.80), understandable (DFCI=5; SCC=4.8), and enjoyable (DFCI=4.33; SCC=3.80). They reported feeling that it took an appropriate amount of time to use the app (DFCI=4.33; SCC=4.20) and were satisfied with the app overall (DFCI=4.33; SCC=4.60). Patients at DFCI who tested the app for 4 weeks took an average of 57.14% of the surveys pushed by the app (median=62.50%). Patients at SCC who had tested the app for 2 weeks took an average of 54.76% of surveys pushed to them (median=64.29%). **This specific study outlined in this protocol will enable pilot testing of the application in Oklahoma, allowing for comparison between patient samples between Boston and Oklahoma.**

D. Research Design and Methods (What, When, How, Where)

STUDY PROCEDURES:

Patients in the Pilot Cohort will pilot the application for 4 weeks (4-week intervention period) and remain on study through the 2-week post-intervention period (6-weeks on study total). The onboarding and monitoring protocol are available in Appendix S. A study team member will contact participants after 4 weeks (end of intervention period), and 6 weeks (end of 2-week post-intervention period). The purpose of these contacts would be to schedule the end of intervention interview and confirm completion of survey assessments (end of 4-week intervention period), as well as the final survey assessments at 6 weeks (end of 2-week post intervention period).

Participants will fall into only one eligibility category:

Table 1: Brief description of pilot cohort activities

Description	Components of Participation

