The Baseline survey will assess socio-demographics, baseline technology use, current comorbidities, current pain management, pain severity, opioid use, pain and psychological symptoms, and quality of life, with metrics shown in Table 4. The end of 4-week intervention period survey will largely replicate the baseline survey; additionally, patients will rate their satisfaction with STAMP+CBT using the 6-item Acceptability E-scale. Surveys will be used to assess pain and psychological symptom trajectory, medication use, and quality of life. See **Appendix P** for the Baseline survey items, **Appendix Q** for 4-week (end of 4-week intervention period) survey items, and **Appendix R** for 2-week (post intervention period) follow-up survey items. Additionally, a subset of patients (up to 15) will be invited for a qualitative interview focused on study burden, facilitators/barriers to app use, satisfaction, and perceived utility in order to guide future refinements to the app (see Appendix T) when they complete use of the app at 4 weeks (end of intervention study period).

Intervention

After the patient completes the baseline survey, a study team member will meet with the patient (in person or virtually), to assist in either 1) downloading the application onto participants' mobile device or 2) providing/mailing the study phone to the participant. The study team member will help to register the patient to the app and help set up any preferences. The study team member will then conduct a 20-30 minute tutorial on the STAMP+CBT app and its intended use (Appendix S). The study team member will also input the patient's pain medications from the EMR, reconciling this list with the patient. The participant will also input their desired goal to work towards for the duration of the trial. During the trial, there is also a survey item that if selected notifies the research team whether a patients' medication or goal needs to be changed and reflected in the app.

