Participants will utilize the STAMP+CBT app for 4-weeks (intervention study period). The 4 weeks will consist of all content introductions. STAMP+CBT hosts and organizes patients' opioid/non-opioid analgesics. It has an extensive multi-media library of education content related to pain management (Appendix A) and pain specific CBT concepts (Appendices A, L, and G). Content will be delivered on a schedule to ensure that patients receive all pain CBT and medication education available (Appendix B). STAMP+CBT prompts patients to take daily surveys to report their pain, pain catastrophizing, mood, opioid/pain medication use, and sleep symptoms and progress towards individualized goals (Appendix B). At the end of each survey, patients receive feedback according to their symptom severity, with links to tailored educational content about pain and psychological symptom management (Table 2, Appendix B). Patients also complete weekly surveys for reporting symptoms listed above as well as goal progress.

If patients report any severe symptoms (Table 3), they are instructed to contact their care team immediately, with a telephone number included on the application screen, see table 2, or to go the Emergency room/call 911 for a true medical emergency. If patients' pain is poorly controlled but not severe enough to be prompted to immediately contact their care team (for example if their average pain is above a 4 and not acceptable), they are reminded to contact their care teams if their symptoms worsen or if they are concerned about it.

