Pain Control	Poor Suboptimal Good
Other Severe Symptoms	Number of severe symptoms on Table 2
Opioids need updating	Yes No
Mood	IF Patient responds to mood questions 17-20 with a total score of ≥ 12 : Low Mood IF Patient responds to mood questions 17-20 with a total score of < 12 : High Mood
Catastrophizing	IF Patient responses to catastrophizing questions 12-16 with a total score greater than ≥ 10 : High Stress IF Patient answers catastrophizing items 12-16 with a total score < 10 : Low Stress
Sleep	If sleep item 23 on the survey score ≥ 3 : Poor If score < 3 : Good
Goals need updating	IF Patient answers “No, it needs to be changed” in goal-setting section of weekly survey: Goal needs updating

Table 3. Severe Symptoms that trigger an email alert to the research team

Pain	
 • Worst pain = 9-10 • Worst pain = 7-10 and new pain
Red Flag Symptoms	
 • Severe weakness or fatigue • Lightheadedness or feeling like I was going to pass out • No gas or stool from my bottom (or ostomy) in the last 2 days • Vomiting 2 or more times in the last 24 hours • Fever of 100.5 or greater • New or worsening chest pain • New or worsening shortness of breath • New or worsening back pain • New numbness and weakness in one or both of your legs • Severe difficulty eating or drinking • Hallucinations/nightmares
Opioid Side Effects	
 • Hallucinations

STUDY TIMELINES

Patients in this Pilot Cohort will be in the research study for 6 weeks total including: a 4-week intervention period and 2-week post intervention period. Patients will use the app for a total of 4 weeks and remain on study through the 2-week post intervention period. They will complete surveys at baseline, 4 weeks (end of intervention period), and at 6 weeks (end of 2-week post intervention period).

We anticipate enrolling 1-2 patients per week during the pilot period, and should this complete the study within 6-8 months.

The study timeline may change due to unforeseen circumstances. The estimated date for the investigators to complete this study (complete primary analysis) is July, 2024.

E. Chart Review

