Statistical analyses will be utilized in this pilot intervention to ascertain feasibility and acceptability of the STAMP+CBT app. We will measure time spent on the app per day and per week, completion rates for surveys and content review, and frequency of app interactions over the course of the pilot. Defined using precision analysis, we will consider the intervention to be **feasible** if $\geq 70\%$ of subjects complete any activity on the app at least 50% of days on study. The intervention will be considered **acceptable** if $>80\%$ of the sample rate the app as satisfactory and useful (4 or higher/5); lower ratings will lead to app and content refinements. Other feasibility measures will assess time to accrual participation rates, and study retention and completion rates. Other acceptability outcomes will be assessed through qualitative debriefing interviews with patients evaluating the perceived benefits, usefulness, and satisfaction of the app, and quantitative acceptability ratings of the app's functionality, perceived utility, ease of use, and content relevance. **Power calculation:** With 35 evaluable patients, we will be able to estimate these proportions with margins of error (half of a 95% confidence interval) of approximately 18% or less assuming that the feasibility threshold of 70% is reached. This margin of error is small enough so that proportion estimates relevant to study feasibility will be accurate and provide informative guidance for future, larger studies. Although power is not sufficient in this pilot, we will explore associations between levels of engagement and changes in pain severity/interference, opioid use, catastrophizing, sleep, mood, and pain self-efficacy.

Because interviews produce qualitative results, statistical analyses will not be employed for a portion of this study. The study team will review qualitative feedback from patients and find common themes related to app feasibility and acceptability. The study team will use the common themes derived from qualitative thematic analysis of the interview that review this feasibility study to guide further iterations of the application and study procedures for future larger, efficacy study of the STAMP+CBT app.

M. Data and Safety Monitoring Plan

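### The feasibility rule counts days over six weeks on study while app use is planned for four, so the bar does not match planned exposure and depends on use after the intervention ends

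*Combined protocol and SAP*

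**What the plan says.** The only numeric criterion for calling the app feasible appears in identical words under Endpoint 1 (Section A) and in Section L, Statistical Methods: at least 70% "of subjects complete any activity on the app at least 50% of days on study". Neither place defines the day count.

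Elsewhere the protocol keeps time on study and time using the app apart:

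- Section D, Study Procedures: participants pilot the app for 4 weeks and "remain on study through the 2-week post-intervention period (6-weeks on study total").
- Study Timelines: "Patients will use the app for a total of 4 weeks and remain on study through the 2-week post intervention period".
- Section D, Survey Assessments: interviews are offered "when they complete use of the app at 4 weeks (end of intervention study period").
- Section D, Intervention: "Participants will utilize the STAMP+CBT app for 4-weeks (intervention study period"), followed by "The 4 weeks will consist of all content introductions".

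Use after week 4 is foreseen. Endpoint 1 will explore "whether app use continues after completion", and Section G (Long Term Follow-up, with Table 4) collects app use at the 6-week survey. Neither place links that use to the 50% rule.

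**The concern.** The per-person bar is a fraction of days, so it is only as meaningful as its denominator. By the protocol's own usage the denominator contains 14 days on which no app use is planned. A participant who engages well for the whole intervention and then stops, as planned, is marked down for those days. A participant who engages little during the intervention but keeps opening the app afterwards is credited for them.

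The rule therefore mixes engagement with the intervention and persistence after it, and persistence is something the plan treats as exploratory. At stake is the headline finding of the pilot, which is meant to inform a future efficacy study.

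**Working it through.** **The plan's own figure.** Section L states a margin of about 18% or less with 35 evaluable patients at 70%. The Wald half-width is 1.96 × √(0.7 × 0.3 / 35) = 15.2 points. The exact interval at 25/35 runs from 53.7% to 85.4%, and its longer arm is 17.7 points. The statement is reproduced. It concerns the share of participants, so the day count does not affect it.

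**Inputs.** On study: 6 weeks = 42 days (Study Procedures, Study Timelines). App period: 4 weeks = 28 days (same places, and Intervention). Day 1 is taken as the start of app use, which is an assumption.

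**Bar for a completer.** Required days = 0.5 × 42 = 21. With k active days in weeks 5 and 6, the bar as a share of app days is (21 − k)/28:

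| Later active days k | App days needed | Share of 28 |
|---|---|---|
| 0 | 21 | 75% |
| 3 | 18 | 64% |
| 7 | 14 | 50% |
| 14 | 7 | 25% |

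Active on all app days and none later: 28/42 = 66.7%. On a 28-day denominator the bar is 14 days.

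**Who changes class.** A completer with d active app days passes on 42 days only with at least 21 − d later days. For d = 14 to 20, the person passes on 28 days but fails on 42 unless at least 7 (d = 14) down to 1 (d = 20) later days are added. For d = 7 to 13, the person fails on 28 days but can pass on 42 with 14 down to 8 later days.

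**Effect on the verdict.** 0.70 × 35 = 24.5, so 25 of 35 must pass. If 60 are evaluable, 0.70 × 60 = 42 must pass. With x of 35 passing on 28 days, x − 24 net downward changes reverse the verdict: 1 if x = 25, 4 if x = 28.

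**Illustration only.** Suppose each person's daily use probability p follows Beta(sm, s(1 − m)) with mean m and s = 4 (range 2 to 8). App-period active days are Binomial(28, p), and later active days are Binomial(14, rp) with r = 0, 0.5 or 1. Average the individual pass probability over p, then take P(at least 25 of 35). At m = 0.70 the individual pass probability is 0.822 on 28 days, and 0.510, 0.712 and 0.820 on 42 days for the three values of r. The probability of a feasible verdict, with the range over s in brackets where given, is:

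| Assumed mean m | 28 days | 42 days, r = 0 | 42 days, r = 0.5 | 42 days, r = 1 |
|---|---|---|---|---|
| 54.76% | 12% (7.5–21%) | about 0% | under 1% | 11% |
| 57.14% | 24% (14–41%) | about 0% | under 1% | 22% |
| 62.5% | 63% (41–86%) | about 0% | 9% (8–11%) | 61% (40–85%) |
| 70% | 96% (84–99.8%) | 1% (0.3–3.5%) | 57% (45–76%) | 96% (83–99.8%) |

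The first two means are the average shares of pushed surveys taken in the Oklahoma and Boston testing (Section C, 5 and 3 testers). The third is the Boston median used here as a mean, and the fourth is assumed. Shares of pushed surveys are not shares of days with any activity, so all four are rough inputs.

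**The case against.** The strongest reply is that the literal rule is not ambiguous for a completer. *On study* means 6 weeks in this protocol, the rule asks for any activity on 21 of 42 days, and nothing excludes activity in weeks 5 and 6. That stands. A reader might infer that the text offers two denominators of equal standing, or that later use is barred from the count. The documents support neither. The nearest support for 28 days is that Section L measures "frequency of app interactions over the course of the pilot" just before the rule. That sentence is about other measures, however, and Study Timelines has the Pilot Cohort in the study for 6 weeks. The 75% figure therefore describes what happens if participants stop using the app. It is not a rival reading of the rule.

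Appendices B (content and survey schedule) and S (onboarding and monitoring) are not in the available file and might show whether the app prompts participants in weeks 5 and 6. That also stands as a limit on what can be said.

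The start of the count is unclear too. Onboarding follows the baseline survey (Section D, Intervention), and baseline may come up to 4 weeks after enrolment (Withdrawal of Subjects). If the count begins at enrolment, 42 and 21 are not exact. This adds to the case for defining the rule.

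Finally, the stakes are modest. This is a single-arm pilot. Endpoint 1 also plans an overall adherence rate with a 95% confidence interval, retention and completion measures, and a judgement that draws on qualitative results. That is a reason to treat the point as a correction to the criterion. It does not remove the mismatch.

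**Conclusion.** The point holds as a mismatch between the headline criterion and planned exposure. Followed literally, and with 42 days counted from the start of app use, a completer must be active on 75% of the app days if use ends with the intervention, and the bar falls only to the extent that use continues beyond it. These day counts need no model.

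Whether the verdict changes depends on behaviour after week 4. At an unchanged daily rate the two denominators give nearly the same answer. With a marked fall in use they can give opposite answers. A reader might infer from the larger contrasts in the table that the literal rule will turn a feasible app into an infeasible one. The documents do not support that. Those contrasts rest on means that are assumed rather than reported and on reduced or absent later use. At the two reported pilot means the threshold is likely to be missed under either denominator.

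The defect should be corrected. It does not undo the pilot.

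**What to change.** In Endpoint 1 and in Section L, replace the phrase *at least 50% of days on study* with *at least 50% (14) of the 28 intervention days, counted from app onboarding*. Keep 28 days as the denominator for every evaluable participant, so that leaving early does not lower the bar. For example, someone who leaves after 10 days with 5 active days meets the current rule at 5/10 = 50%, but has 5/28 = 18% under the fixed denominator. Report app use in weeks 5 and 6 separately and descriptively.

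This is best settled before engagement data are examined. Study staff check engagement on the dashboard twice daily, Monday to Friday (Section D, Intervention), so that may no longer be possible. If engagement data have been seen, report the 28-day and 42-day results side by side and state that the denominator was fixed afterwards.

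The cost is wording in two places and one tabulation. The change does not favour the sponsor or work against it uniformly: for completers with little later use, 28 days is an easier bar than the literal rule, and for early leavers it is stricter. The report should say so. The stated 18% margin does not change.

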The study team will complete a limited structured chart abstraction at baseline and at end-of-study to collect basic non-identifiable clinical/demographic information (See appendix O). Chart abstraction will assess clinical actions responding to STAMP+CBT data and healthcare utilization related to pain and symptom management (e.g., hospitalization, ER visits, urgent clinic visits for symptom management, psychosocial oncology social work, psychology, or psychiatry visits). As people with cancer have variable prognoses, they may pass away during a study; therefore, we want to be able to abstract and record if/when a patient passes away during or recently after their involvement. Should this situation arise, it can negatively influence outcomes of the study evaluation (feasibility/acceptability).

Chart abstraction information collected will include the following:

- **Demographics:** Gender, age, ethnicity, race
- **Cancer:** Patient's date of diagnosis, diagnosis (cancer type), stage at diagnosis, status of active curative or palliative treatment, history and date of surgery related to cancer, and whether patient has seen palliative care (yes/no)
- **Pain:** patient's last pain rating, type of pain, location of pain, surgeries or operations for pain, documented calls about pain.
- **Prescribed Pain Medicines:** Patient's prescribed short-acting opioid, long-acting opioid, and non-opioid pain medications, and length of time taking opioids.
- **Prescribed Anxiolytics:** Patients' prescribed anxiolytics and whether this was prescribed before or during the study
- **Prescribed Antidepressants:** Patients' prescribed antidepressants and whether this was prescribed before or during the study
- **Medication/Opioid side effects:** Constipation or related symptoms.
- **Clinic visits:** Unplanned or urgent clinic visits that include pain 6 months prior, during, and 6 months post-intervention, and social work, psychology, or psychiatry visits during study period
- **Mental Health Diagnoses:** Whether the patient has a mental health diagnosis and what mental health diagnosis the patient has

F. Biospecimens

This study does not involve any specimen collection/banking of any kind. Personal health information will be collected as part of the study. The consent

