- Cognitive impairment that would interfere with study participation, as judged by treating clinician
- Inability to speak English (the intervention has not yet been translated to Spanish)
- Enrolled in hospice
- Currently hospitalized
- Use of transmucosal fentanyl, given safety concerns and ongoing risk mitigation program required to prescribe these (TIRF REMS)
- Pain primarily related to a recent surgery (within the last 2 weeks)

We will exclude adults who are unable to consent, individuals who are not yet adults (infants, children, teenagers), pregnant women, and prisoners.

WITHDRAWAL OF SUBJECTS

Subjects who do not complete the baseline assessment within 4 weeks of study enrollment will be withdrawn from the research study without their consent and considered non-evaluable for the primary endpoint. Non-evaluable subjects will be replaced until the total evaluable subject accrual of 35 participants is met.

These patients will be informed of their withdrawal from the study by study staff. The study PI, [name], will make all decisions regarding early termination of the study. The study team will then notify all participants accordingly.

Patients will be notified by study staff if they will be partially withdrawn from the research, as reviewed in their consent form (Appendix AD) as well.

I. Gender/Minority/Pediatric Inclusion for Research

Potential participants will not be excluded based on gender or race/ethnicity, though note that English fluency will be required as many assessments that will be used in the present study are not available in other languages. We will exclude

adults who are unable to consent, individuals who are not yet adults (infants, children, teenagers), pregnant women, and prisoners.

J. Recruitment and Enrollment

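### Must the plan say whether an evaluable patient with no 4-week rating stays in the denominator of the >80% acceptability rule?

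*Combined protocol and SAP*

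**What the plan says.** The acceptability rule appears twice in the same words, in section A (Endpoint 1) and section L (Statistical Methods). The app is acceptable if more than 80% "of the sample rate the app as satisfactory and useful (4 or higher/5); lower ratings will lead to app and content refinements". The sample is not defined further.

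The precision statement in both sections covers the feasibility and acceptability proportions together: "With 35 evaluable patients, we will be able to estimate these proportions with margins of error (half of a 95% confidence interval") of about 18% or less, assuming the 70% feasibility threshold is reached.

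Section H (Withdrawal of Subjects) gives one ground for being non-evaluable, which is not completing the baseline assessment within 4 weeks of enrolment. Such patients are "considered non-evaluable for the primary endpoint. Non-evaluable subjects will be replaced until the total evaluable subject accrual of 35 participants is met". Aim 1 and Table 1 allow enrolment of up to 60; the Abstract gives n=60.

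The rating comes later. Section D (Survey Assessments) says of the 4-week survey that "additionally, patients will rate their satisfaction with STAMP+CBT using the 6-item Acceptability E-scale", and Table 4 marks satisfaction at T2 only.

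Section E (Chart Review) expects some loss: "As people with cancer have variable prognoses, they may pass away during a study", and if so "it can negatively influence outcomes of the study evaluation (feasibility/acceptability"). It gives no counting rule.

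**The concern.** Evaluability is settled at baseline and the rating is taken four weeks later. A patient can therefore be evaluable, not be replaced, and leave no rating. The sample could then mean all evaluable patients, with a missing rating counting against the app, or only those who returned the 4-week survey. With a hard threshold and about 35 patients, the two readings can give opposite verdicts on the same data.

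Acceptability is half of the primary objective, and a low result triggers app refinements. If the base were chosen after the ratings were seen, that choice could decide the answer. The raters-only base would also flatter the app if dissatisfied patients returned the survey less often.

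**Working it through.** **1. The plan's own figure.** Inputs from section L: n = 35, p = 0.70. The Wald half-width is 1.96 × √(p(1−p)/n) = 1.96 × √(0.21/35) = 15.2 points. The exact (Clopper-Pearson) interval is asymmetric; its lower arm is 17.9 points at 24/35 and 17.7 at 25/35. The Wald half-width with continuity correction at the worst case p = 0.5 is 18.0. The claim of about 18% or less reproduces. At p = 0.80 with 29 raters, 1.96 × √(0.16/29) = 14.6 points, so moderate loss of ratings does not break it.

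**2. Counts needed to exceed 80%.** The rule needs the smallest whole number strictly above 0.80 × denominator. With all 35 as the base this is 29, since 28/35 = 80.0% exactly. Assuming exactly 35 evaluable patients:

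| Ratings missing | Raters | Needed, raters only | Needed, all 35 | Counts where the verdicts differ |
|---|---|---|---|---|
| 0 | 35 | 29 | 29 | none |
| 1 | 34 | 28 | 29 | 28 |
| 3 | 32 | 26 | 29 | 26–28 |
| 6 | 29 | 24 | 29 | 24–28 |
| 7 | 28 | 23 | 29 (out of reach) | 23–28 |

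**3. How often the readings would differ.** The documents give no satisfaction rate and no 4-week return rate, so both are assumed here. If 85% of raters are favourable and patients return the survey at random, P(acceptable) for raters only versus all 35 is 77.2% v 47.7% at 95% return, 77.9% v 25.2% at 90%, and 76.1% v 3.9% at 80%. Passing on all 35 implies passing among raters, so the chance of disagreement is the difference: 29.5%, 52.7% and 72.2%.

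**4. Selective return.** Assume 70% of all 35 are satisfied and satisfied patients return at 95%. The raters-only rule then passes in 58.5%, 30.1%, 19.9% or 9.0% of trials when dissatisfied patients return at 50%, 70%, 80% or 95%. The all-35 rule passes in 2.6% throughout. The size of this bias depends almost wholly on the return rate assumed for dissatisfied patients.

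**5. What the cut-offs rest on.** The 35 in the table is the level to which non-evaluable patients are replaced; the plan does not say that accrual closes there, and up to 60 may enrol. With 60 evaluable, 49 favourable ratings are needed (48/60 = 80.0%), and it takes 12 missing ratings to put the all-evaluable rule out of reach, not 7.

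**6. Is there a return rate in the preliminary data?** Section C says "We have completed initial user acceptability testing of the app with patients from our target population (n=6) at the SCC", then reports ratings thus: "Patients who have tested the app to date (DFCI pilot, n=3; SCC pre-pilot, n=5) have reported finding the app easy to use". It does not say that the sixth SCC tester failed to return a rating. Even read that way, 1 of 6 has an exact 95% interval of 0.4% to 64.1%, so it cannot serve as an attrition estimate.

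**The case for a change.** The strongest case for a change is that the fix is cheap and its timing matters. One sentence, written before any rating is seen, would remove the analyst's freedom to pick the base. The precision statement points towards 35, but it is not a definition of the sample. Nor does it secure 35 ratings. Section H ties evaluability to the primary endpoint, and Aim 1 names feasibility alone as the primary outcome, so that definition may not reach acceptability at all. The gift card for the 4-week survey and the staff contact at that point should reduce non-return but cannot prevent loss through death or withdrawal.

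Much of this stands. The text is silent on missing ratings, the arithmetic is right, and a sentence would be tidy. What does not stand is the step from silence to error. Endpoint 1 contains both rules, and the same 35 is applied to both proportions, so the text does not settle the base for feasibility while leaving it open for acceptability. Both rest on the same evaluable group, and only the handling of a missing rating is left unsaid. Neither answer is plainly better: counting a patient who died as dissatisfied mixes survival with opinion of the app, while dropping non-returners may favour the app. That is a fair trade-off for the team.

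**Conclusion.** No change follows. This is an unwritten detail that analysts can fill sensibly, and it contradicts no number or rule in the plan. Section L already reports survey completion and study retention, and deaths are abstracted from the chart. The number of missing ratings and its link to death will therefore be known, and the share among raters can be shown beside the share among all evaluable patients.

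The consequence is also limited. The two readings differ only when ratings are missing and the favourable count falls in a band: the single count 28 with one missing of 35, or 24 to 28 with six missing. A result below the threshold leads to refinements, but Endpoint 1 plans a final modification of the app from the results in any case, and it judges acceptability on qualitative and quantitative findings together. Enrolment of up to 60 leaves room for 60 − 35 = 25 patients beyond the replacement target.

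The cut-offs in the table assume exactly 35 evaluable patients. The probabilities assume satisfaction and return rates that the documents do not give. If ratings are complete, the question does not arise. The difference between n=60 in the Abstract and up to 60 elsewhere is a matter of wording and does not bear on this point.
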